**Secondary Outcome Measures:****Safety Endpoints:**

- Proportion (%) of patients with any AEs, SAEs and drug-related AEs during the study (Baseline to Day 14 and Day 28)
- Proportion (%) of patients with clinically significant abnormality in clinical laboratory tests and ECG during the study (Baseline to Day 14 and Day 28)
- Change in parameters for coagulopathy including [REDACTED] during the study (Baseline to Day 14 and Day 28)
- Change in parameters of cardiac function including [REDACTED] during the study period (Baseline to Day 14 and Day 28)

Changes in safety outcomes in patient populations with different Baseline levels of inflammatory biomarkers to assess the correlation of biomarker profile to safety outcomes.

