## 3. Trial Design

### 3.1. Overall Design

This will be a multicenter, randomized, double-blinded, placebo-controlled study to evaluate safety and efficacy of SIR1-365 in hospitalized patients with severe COVID-19. The primary objective is to assess the overall safety and tolerability of SIR1-365 administered orally at 100 mg, three times per day (TID) for up to 14 consecutive days relative to the placebo group. The secondary objectives are to assess the effects of SIR1-365 on clinical efficacy endpoints, and the biomarkers indicative of inflammation, target engagement and kidney injury as well as SIR1-365 PK.

Approximately 60 eligible patients will be randomly assigned at a 1:1 ratio to receive either SIR1-365 at 100 mg, TID or matching placebo for up to 14 consecutive days. Patients could be hospitalized for up to 14 days. Patients will be assessed daily while hospitalized. If the patients are discharged from the hospital before Day 14, all the assessments planned for Day 14 should be carried out before discharge. If a patient is still hospitalized after Day 14, no study drug will be administered after the last dose on Day 14.

It is preferred that the follow-up visit is in person to obtain safety laboratory tests. However, infection control or other restrictions may limit the ability of the patients to return to the clinic. In this case, the follow-up visit may be conducted by phone and only safety data will be obtained. Study drugs will not be administered for early discharged patients.

All randomized patients will receive standard supportive medical care for treatment of COVID-19 throughout the study. Follow-up visit will be scheduled approximately on Day 28 ( $\pm 3$ ) or 14 ( $\pm 3$ ) days after the last dose for those who are discharged from the hospital before Day 14.

SIR1-365 will be administered orally either as intact tablets with water if patient can swallow or as disintegrated suspension form to be delivered via a nasogastric (NG) tube if patient cannot swallow. Food and water will be allowed as needed.

[figure not shown]
To fit into the clinical practice of treating patients with severe COVID-19, screening visit and baseline visit can be combined in some patients. In that case, the number of dosing could be less than 3 times on that day. ECG, laboratory test and other test results obtained within 24 hours prior to consent can be used as baselines.

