### **7.2.1. Follow-up for Patients Who Discontinued from Treatment/Study**

If the patients are discharged from the hospital before Day 14, it is preferred that the follow-up visit is in person to obtain safety laboratory tests and blood samples for biomarker analysis as well as clinical outcome data. However, infection control or other restrictions may limit the ability of the patients to return to the clinic. In this case, the follow-up visit may be conducted by phone and only safety data will be obtained.

Patients who complete the 14-day treatment should be instructed to have the scheduled follow-up visit on Day 28. If a patient determines he/she no longer wishes to participate in follow-up visit, all the procedures associated with Day 28/Early Discontinuation/End of Study (EOS) visit should be completed at the time of discontinuation.

In both cases, follow-up for AEs should occur as per the discretion of the investigator. It is vital to obtain follow-up data on any patient withdrawn because of an AE or SAE. In every case, efforts must be made to undertake protocol-specified safety follow-up procedures.

Refer to the schedule of assessments (SoA) for data to be collected at the time of study discontinuation, follow-up, and for any further evaluations that need to be completed.

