#### **8.2.2.1. Period and Frequency for Collecting AE and SAE Information**

All AEs and SAEs will be collected from the time when ICF is signed until the end of the patient's participation in the study.

All SAEs will be recorded and reported within 24 hours, as indicated in [Appendix 4](#). The Investigator will submit any updated SAE data within 24 hours of it being available. The SAE should be entered to EDC as defined in [Appendix 4](#).

Investigators are not obligated to actively seek AE or SAE in former study patients. However, if the Investigator learns of any SAE, including a death, at any time after a patient has been discharged from the study, and he/she considers the event to be reasonably related to the study treatment or study participation, the Investigator must promptly notify the sponsor.

The method of recording, evaluating, and assessing causality of AE and SAE and the procedures for completing and transmitting SAE reports are provided in [Appendix 4](#).

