#### **8.2.2.3. Follow-up of AEs and SAEs**

After the initial AE/SAE report, the Investigator is required to proactively follow each patient at subsequent visits/contacts. All SAEs, and non-serious AEs of potential interests, will be followed until resolution, stabilization, until the event is otherwise explained or the patient is lost to follow-up (as defined in [Section 7.3](#)). Further information on follow-up procedures is given in [Appendix 4](#).

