- Patient incidence of TEAEs occurring with onset \leq 7 days, onset \leq 14 days and onset \leq 28 days of first dose by MedDRA SOC, PT, and closest relationship to study drug (Definitely Related/ Probably Related/ Possibly Related/ Unlikely Related/ Unrelated). At each level of patient summarization, a patient is classified according to the closest relationship if the patient reported 1 or more events. Adverse events with a missing relationship will be considered definitely related for this summary.
- Patient incidence of drug-related TEAEs occurring with onset \leq 7 days, onset \leq 14 days and onset \leq 28 days of first dose by MedDRA SOC and PT
- Patient incidence of drug-related TEAEs occurring with onset \leq 7 days, onset \leq 14 days and onset \leq 28 days of first dose by MedDRA SOC, PT, and highest toxicity grade
- Patient incidence of treatment-emergent SAEs occurring with onset \leq 7 days, onset \leq 14 days and onset \leq 28 days of first dose by MedDRA SOC and PT
- Patient incidence of TEAEs leading to study drug discontinuation with onset \leq 7 days, onset \leq 14 days and onset \leq 28 days of first dose by MedDRA SOC and PT
- Patient incidence of deaths with onset \leq 7 days, onset \leq 14 days and onset \leq 28 days of first dose by MedDRA SOC and PT
- Listing of SAEs (presented in the Table section of the appendices)

- Listing of AEs resulting in study drug discontinuation (presented in the Table section of the appendices)
- Listing of AEs resulting in death (presented in the Table section of the appendices)

All AEs will be listed. An additional listing of all AEs of potential interest will also be created.

AEs will be analyzed descriptively including 2-sided 95% CI for between-group (SIRI-365 – placebo) incidence rates. Incidence rates among treatment groups will be compared using the Fisher exact test. AEs analyzed will include, but not necessarily limited to following:

- At least 1 AE with onset \leq 7 days of first dose
- At least 1 AE with onset \leq 14 days of first dose
- At least 1 AE with onset \leq 28 days of first dose
- At least 1 TEAE with onset \leq 7 days of first dose
- At least 1 TEAE with onset \leq 14 days of first dose
- At least 1 TEAE with onset \leq 28 days of first dose
- At least 1 Drug-Related TEAE
- At least 1 SAE
- At least 1 TEAE of Severe Intensity
- AE leading to study drug discontinuation
- Death

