Additionally, the Exposure Adjusted Incidence Rate (EAIR) of AEs will be summarized by treatment group. The EAIR of AEs is calculated as the number of subjects with an event (preferred term), divided by the total exposure time of all subjects at risk of an initial occurrence of that event. For a subject who never experiences the event, the exposure time is calculated as the duration between the date/time of first study drug administration, to the date of last follow-up assessment (end of study participation). For subjects with at least one occurrence of an event, the exposure time is the duration between the date/time of first study drug administration, to the date/time of the first occurrence of that event.

This will be presented as the number of subjects reporting the event and calculated EAIR in person-weeks.

A similar summary will be provided of the EAIR of related AEs by preferred term.

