13.1.6 Patients with respiratory failure

Respiratory failure is defined as need for mechanical ventilation, ECMO, noninvasive ventilation, or high-flow nasal cannula oxygen delivery (heated, humidified, oxygen delivered via reinforced nasal cannula at flow rates >20 L/min with fraction of delivered oxygen ≥ 0.5). Other oxygen requirements recorded in the “Other, Specify” field of the eCRF

will be reviewed for any other criteria that may qualify. Any such cases will be identified prior to database lock and unblinding.

The number and percentage of patients with respiratory failure at any time from Baseline to Day 28 will be summarized by treatment. Associated 95% CI for the proportion of respiratory failure will be provided for each treatment group using Clopper-Pearson method. Patients without any post baseline oxygen requirement data recorded will be considered free of respiratory failure.

Changes in O₂ requirements which are considered to be respiratory failure will be flagged in the data listing.

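### For patients discharged before Day 14 the only scheduled contact can fall well before Day 28, yet mortality, respiratory failure and AE/SAE incidence are reported as crude Day 28 proportions

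*Protocol*

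**What the plan says.** **Follow-up timing.** Protocol 3.1 (also the Synopsis, Protocol section 8 and SAP section 5) sets one follow-up visit at about Day 28 (±3), or 14 (±3) "days after the last dose for those who are discharged from the hospital before Day 14". Protocol 7.2.1 adds: "Patients who complete the 14-day treatment should be instructed to have the scheduled follow-up visit on Day 28". No study drug is given after discharge, daily assessment is in hospital only, and the Schedule of Assessments has a single post-treatment column.

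**Collection after that visit.** Under Protocol 8.2.2.1, AEs and SAEs are collected until participation ends, after which "Investigators are not obligated to actively seek AE or SAE in former study patients". A later SAE must be reported only if the investigator learns of it and considers it reasonably related to study treatment or participation.

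**Endpoints with a Day 28 horizon.**
- AE/SAE incidence, a secondary safety measure: "Proportion (%) of patients with any AEs, SAEs and drug-related AEs during the study (Baseline to Day 14 and Day 28"). SAP 11.2 tabulates events with onset up to 28 days and states: "Incidence rates among treatment groups will be compared using the Fisher exact test". SAP section 8 makes the whole analysis set the denominator in AE tables.
- Respiratory failure (SAP 13.1.6): "The number and percentage of patients with respiratory failure at any time from Baseline to Day 28 will be summarized by treatment".
- All-cause mortality (SAP 13.1.7): a proportion from Baseline to Day 28 with a Clopper-Pearson interval.

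**The concern.** The endpoints look to Day 28, but the schedule for early-discharged patients does not. A death, a readmission with respiratory failure, or a new unrelated SAE after the last scheduled contact is not actively sought.

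The SAP has no rule for such patients. The missing-data provisions in SAP 12.4 do not cover mortality, respiratory failure or AE incidence. The one rule in SAP 13.1.6 is for patients with no post-baseline oxygen data at all, which an early-discharged inpatient would ordinarily have. SAP section 8 leaves missing values out of percentages in general, but no unknown-status category is defined for these endpoints. In a tabulation of recorded events, no record reads as no event.

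Discharge day and last-dose day are themselves outcomes of treatment. If the drug changes them, the arms are watched for different lengths of time and the arm discharged sooner can look better for that reason alone. If timing is equal, both arms' Day 28 rates are too low. That matters a little because Protocol 10.1 intends the estimates for planning later studies.

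**Working it through.** **1. The plan's own calendar.** For completers it is consistent: 14 + 14 = Day 28, and 7 screening days + 28 = 35 days, the total duration in Protocol 3.1.

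**2. Early discharge.** With last dose on Day d, the nominal contact is d + 14, the window is d + 11 to d + 17, and the nominal shortfall to Day 28 is 14 − d.

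| Last dose (day) | Nominal contact | Window | Days short of Day 28 |
|---|---|---|---|
| 3 | 17 | 14–20 | 11 |
| 5 | 19 | 16–22 | 9 |
| 7 | 21 | 18–24 | 7 |
| 10 | 24 | 21–27 | 4 |
| 13 | 27 | 24–30 | 1 |

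For d = 1 to 7 the latest contact is Day 24 or earlier, so the completers' window of Days 25 to 31 cannot be reached. For d = 8 to 10 it is reached only by using the +3 allowance. For d = 11 to 13 the nominal contact lies inside it. The anchor is the last dose, not discharge: a patient who stops drug on Day 3 and goes home on Day 12 is due on Day 17. None of this needs an assumption.

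**3. Primary endpoint.** The nominal contact is never before Day 15. The window opens before Day 14 only for a last dose on Day 1 or 2 (Days 12 and 13).

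**4. Size of the distortion.** The documents give no discharge distribution and no late event risk, so the following is assumed:
- 30 patients per arm, with equal true risk in both arms;
- k1 and k2 early-discharged patients per arm, each with last dose on Day 7 and contact on Day 21;
- constant hazard over Days 15 to 28, with risk q of a first event in that period for an early-discharged patient.

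Contact on Day 21 covers 7 of those 14 days, so the captured risk is 1 − (1 − q)^0.5 and the missed risk is m = q − captured. The between-arm distortion is (k1 − k2)/30 × m.

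Example, q = 10%, k1 = 20, k2 = 10: captured = 1 − 0.90^0.5 = 5.13%; m = 4.87%; 10/30 × 4.87% = 1.62 points; × 30 = 0.49 patients.

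| Early-discharged, arm 1 vs arm 2 | q = 2.5% | 5% | 10% | 20% |
|---|---|---|---|---|
| 20/30 vs 10/30, points | 0.4 | 0.8 | 1.6 | 3.1 |
| the same, in patients | 0.12 | 0.25 | 0.49 | 0.94 |
| 15/30 vs 10/30, points | 0.2 | 0.4 | 0.8 | 1.6 |

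The columns 5%, 10% and 20% apply a general late risk equally to everyone. The columns 2.5%, 5% and 10% are the same three cases if early-discharged patients carry half that risk.

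The absolute under-count within an arm is k × m. With 10/30 discharged early in both arms and q = 10%, each arm misses 10 × 4.87% = 0.49 events (1.6 points) and the difference is zero. In the largest case above (q = 20%, m = 9.44%), the arm with 20 early discharges misses 20 × 9.44% = 1.9 events, against 0.94 in the other.

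For scale, the planned Clopper-Pearson interval for 3/30 is 2.1% to 26.5%.

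**The case against.** Much of the case on the other side is sound.

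- **Small and exploratory.** The sample size is not based on power, and SAP 13.1.6 and 13.1.7 plan only per-arm intervals, although SAP 11.2 does list death among the items compared by Fisher's test. The scenarios lean high: 20/30 against 10/30 means twice as many early discharges, and patients fit to go home probably carry less late risk. For any-AE incidence, many patients will already be counted from their hospital stay, so the loss is smaller still. This stands and limits the point to a minor one.
- **The schedule is defensible.** Last dose + 14 days gives every patient the same off-drug safety window. This stands, and the visit should be kept.
- **Other provisions help.** Under Protocol 8.2.2.3, "All SAEs, and non-serious AEs of potential interests, will be followed until resolution, stabilization, until the event is otherwise explained"; that covers events already open, not new ones. Protocol 7.2.1 asks for efforts at safety follow-up. The exposure-adjusted rate in SAP 11.2 runs "to the date of last follow-up assessment (end of study participation"), but it is by preferred term and does not adjust the Fisher comparisons, mortality or respiratory failure. The Day 28 LOCF table for the WHO scale (SAP 12.4, 13.1.4) can use the earlier visit. Protocol 9.9 carries Day 28 in its heading but sets no separate timing for early-discharged patients.

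A reader might infer more than the documents support:
- *That early-discharged patients are never heard of again.* The visit is the only scheduled contact, not the only possible one.
- *That the SAP instructs analysts to score them event-free.* It is silent; the result follows from counting recorded events.
- *That the bias is large.* If every patient were discharged early, with last dose on Day 5 in one arm and Day 8 in the other, and constant hazard from Day 1, a true 60% Day 28 risk would appear as 46.3% vs 51.3%. Nothing in the documents suggests universal early discharge, and events in hospital would not follow that hazard.

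**Conclusion.** The mismatch is real and rests on the plan's own calendar. Patients discharged early can finish scheduled observation up to 13 days before Day 28 (last dose on Day 1), and the Day 28 proportions for mortality, respiratory failure and AE/SAE incidence make no allowance for it. Its direction is predictable: late events are under-counted, and more so in the arm discharged sooner.

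Its size is modest. The between-arm figures in the table rest wholly on the assumed discharge split, last-dose day and late hazard, and none reaches one patient in 30. It does not threaten the trial's primary conclusion. The grade is minor: a cheap improvement worth making, because late status that is not collected may be hard to recover.

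**What to change.** **Protocol.** Keep the last dose + 14 visit and add a brief Day 28 (±3) phone contact for every early-discharged patient, recording vital status, AEs/SAEs, readmission and oxygen use.

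**SAP.** For mortality, respiratory failure and the Day 28 AE/SAE proportions, report by arm the number of patients with unknown Day 28 status, and do not count them as event-free. If the call is not added, or is missed, give a supportive estimate censored at last contact: Kaplan-Meier for death, and cumulative incidence with death competing for respiratory failure and AE/SAE. Label it supportive, because the patients censored early are those well enough to leave, so it may err upwards.

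**Wording.** Reconcile the follow-up timing in Protocol 3.1, 7.2.1 and 9.9, SAP section 5, and section 4 of the PK/PD analysis plan, which anchors the visit to discharge or end of treatment instead of the last dose.

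**Cost.** One short call per early-discharged patient, plus a protocol amendment with IRB approval and re-consent (Protocol section 13). The SAP changes alone need no protocol amendment.

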### **3.2. Scientific Rationale for Trial Design**

The randomized, double-blind, placebo-controlled design is considered the most convincing research design. Randomization eliminates the influence of unknown or immeasurable confounding variables and blinding eliminates confounding by cointerventions, thus minimizing bias and incorrect estimate of treatment effect. The main reason to have a placebo group is to be sure that any observed effects are actually caused by the test drug but not some other factors.

For ethical and medical reasons, standard of care treatments for COVID-19 will be provided to all patients. Study treatments (either SIR1-365 or matching placebo) will be given as add-on therapy.

### 3.3. Justification for Dose Selection

In the mouse SIRS study, oral administration of SIR1-365 at [REDACTED] resulted in about 50%, 75% and 100% survival rate, respectively. The mean plasma  $C_{max}$  levels for the 3 doses were [REDACTED] respectively. Since in vitro cell function assays have shown that the potency of SIR1-365 is about [REDACTED] higher in human cells than mouse cells, the approximate plasma levels of SIR1-365 to achieve similar effects in human could be around [REDACTED] ng/ml.

Based on the PK data obtained from the completed MAD study in healthy adult subjects, the trough levels with 100 mg, TID were [REDACTED] between day 1 and day 10, respectively, which is between the estimated human exposure to [REDACTED] survival rate. The peak levels with 100 mg TID ranged from [REDACTED] which is above the EC50 [REDACTED] P1 inhibition. Therefore, the initial dose chosen for this study is 100 mg, TID (or 300 mg per day).

The  $AUC_{0-8}$  with 100 mg TID ranged from [REDACTED] or  $AUC_{0-24}$  around [REDACTED] [REDACTED] g/mL). Since the observed  $AUC_{0-24}$  with NOAEL dose [REDACTED] 8-day GLP studies in monkeys was [REDACTED] the dose of 100 mg TID should have a safety margin between [REDACTED] on an AUC basis.

Based on the safety, preliminary efficacy, biomarker and PK results of 100 mg TID dose, additional dose(s) may be added for further evaluation.

#### 4. Objectives and Outcome Measures

Objectives	Outcome Measures
Primary	
Primary Objective: To assess the overall safety and tolerability of SIR1-365 in patients with severe COVID-19	Primary Safety Measure 
 
Proportion (%) of patients with any TEAEs during the treatment period (Baseline to Day 14)
 
 Secondary Safety Measures 
 
Proportion (%) of patients with any AEs, SAEs and drug-related AEs during the study (Baseline to Day 14 and Day 28)
 
Proportion (%) of patients with clinically significant abnormality in clinical laboratory tests and ECG during the study (Baseline to Day 14 and Day 28)
 
[REDACTED]
 
[REDACTED]
 
 
Changes in safety outcomes in patient populations with different Baseline levels of inflammatory biomarkers to assess the correlation of biomarker profile to safety outcomes.

Secondary	
1. To assess the clinical efficacy of SIR1-365 in patients with severe COVID-19	Clinical Efficacy Endpoints 
 
Change from Baseline to Day 7 and Day 14 in PaO2/FiO2 ratio
 
Time to improvement of oxygenation defined as oxygen saturation (pulse oximetry) >93% and increased by ≥1% from Baseline breathing only room air in the 48 hours preceding the measurement during the study (Baseline to Day 28)
 
Number of days without oxygen use during the study (Baseline to Day 28)
 

Objectives	Outcome Measures
	
 
Change from Baseline to Days 7, 14 and 28 in the score of the WHO ordinal scale
 
Proportion (%) of patients with clinical improvement defined as a reduction of 2 points in the WHO ordinal scale during the study (Baseline to Day 28).
 
Number of days hospitalized during the study (Baseline to Day 28)
 
Proportion (%) of patients free of respiratory failure during the study (Baseline to Day 28)
 
All-cause mortality rate during the study (Baseline to Day 28)
 
 
Changes in clinical efficacy endpoints in patient populations with different Baseline levels of inflammatory biomarkers to assess the correlation of biomarker profile to clinical efficacy outcomes

2. To assess the effects of SIR1-365 on multiple inflammatory biomarker levels including CRP, ferritin, lymphocyte and neutrophil counts, cytokines and chemokines	
Inflammatory Biomarker Measures
 
 
Change from Baseline to Day 7 and Day 14 in [REDACTED] levels
 
Time and number of the patients to reach 50% reduction from Baseline in [REDACTED] during the treatment period (Baseline to Day 14)
 
Change from Baseline to Day 7 and Day 14 in inflammatory biomarker [REDACTED] lymphocytes and neutrophil to lymphocyte ratio.
 
[REDACTED]
 
[REDACTED]
 

3. To assess the effects of SIR1-365 on biomarkers indicative of kidney injury	
Biomarker Assessment for Kidney Injury
 
 
Change from Baseline to Day 7 and Day 14 in [REDACTED]
 

Objectives	Outcome Measures
in patients with severe COVID-19	
 
• Change from Baseline to Day 7 and Day 14 [REDACTED]
 

4. To assess the effects of SIR1-365 on biomarkers indicative of vascular endothelial cell damage in patients with severe COVID-19	Biomarker Assessment for CV Endothelial Cell Damage 
 
• Change from Baseline to Day 7 and Day 14 in [REDACTED]
 
• Change from Baseline to Day 7 and Day 14 in [REDACTED]
 
• Change from Baseline to Day 7 and Day 14 in [REDACTED]
 

5. To assess the effects of SIR1-365 on biomarkers indicative of target engagement in patients with severe COVID-19	Biomarker Assessment for Target Engagement 
 
• Change from Baseline to Day 7 and Day 14 in [REDACTED]
 
• Change from Baseline to Day 7 and Day 14 in [REDACTED]
 
 
Additional biomarkers may be assessed as appropriated. Details about sample collection and biomarker analysis will be provided in laboratory manual.

6. To measure plasma SIR1-365 levels in patients with severe COVID-19	Measurement of Plasma SIR1-365 and metabolite Levels One blood sample will be collected from each patient within 30 min before and 2 hours ( $\pm 5$ min) after the 1 st dose on Day 1, respectively. On Days 7 and 14, one blood sample will be collected within 30 min before and 2 hours ( $\pm 5$ min) after the 2 nd dose, respectively. Plasma SIR1-365 and metabolite levels will be measured by validated bioanalytical method following GLP guidance.

